## **8.1. Administrative baseline procedures**

### **8.1.1. Collection of demographic data**

Record demographic data such as year of birth, sex, race, and ethnicity in the participant's eCRF.

Collection of sex, race and ethnicity data is necessary to assess and monitor the diversity of the trial participants, and to determine if the trial participants are truly representative of the impacted population.

### **8.1.2. Medical/vaccination history**

Obtain the participant's medical/vaccination history by interviewing the participant and/or review of the participant's medical records. Record any pre-existing conditions, signs and/or symptoms present prior to the study intervention administration and flu vaccination history for the past 2 years in the eCRF.

### **8.1.3. Provision of eDiary device or installing of eDiary application on participant's personal device**

Participants will be encouraged to bring their own personal electronic devices (e.g., smart phone or tablet) to the screening visit (in Phase 1 only) or to Visit 1 (Day 1 in Phase 1 and Phase 2). The study staff will check the compatibility of the participant's device with respect to the eDiary application.

At Visit 1 (Day 1), with support from the study staff, the participant will download the eDiary application on his/her own electronic device. For participants who do not wish to use their own device for study purposes or whose device is incompatible with the eDiary

application, will be provided an electronic device by the study staff. The provisioned devices will have the study eDiary application already installed.

The eDiary application will be used by the participant to self-report information related to his/her health post-dosing (e.g., solicited events, responses to the **CCI**). The study staff will train the participant on the use of the eDiary and emphasize the importance of completing the eDiary throughout the eDiary data collection period.

The study staff will train the participant and/or his/her caregiver (if identified by the study participant) on the use of the eDiary.

Refer to Section [8.4.1](#) for details of collection of safety information and Section [10.3.5](#) for guidelines.

## **8.2. Immunogenicity assessments**

Planned timepoints for all immunogenicity assessments are provided in the SoA.

Biological samples will be used for research planned in the protocol and for purposes related to the improvement, development and quality assurance of the laboratory tests described in this protocol.

Findings in this or future studies may make it desirable to use samples acquired in this study for research not planned in this protocol. In this case, all participants in countries where this is allowed will be asked to give consent to allow GSK or a contracted partner, to use the samples for further research. The further research will be subject to prior IEC/IRB approval, if required by local legislation.

Information on further research and its rationale can be obtained from GSK.

Sample testing will be done in accordance with the recorded consent of the individual participant.

By default, collected samples will be stored for a maximum of 20 years. This storage period begins when the last participant performs the last study visit. This timeline can be adapted based on local laws, regulations or guidelines requiring different timeframes or procedures. In all cases, the storage period should be aligned with participant's consent. These additional requirements must be formally communicated to, discussed and agreed with GSK.

### **8.2.1. Biological samples**

Approximate amount of blood collected from each participant, over the duration of the study, is summarized in the SoA (Section [1.3](#)) and [Table 10](#).

**Table 10 Approximate volume of blood collected at each time point and during the whole study**

	Sample type	Day - 28 to Day 1	Day 1	Day 2	Day 8	Day 29	Day 92	Day 183	Total
Phase 1	Blood	10 mL	40 mL	-	10 mL	40 mL	30 mL*	30 mL*	160 mL
Phase 1	Urine**	As per local practice							
Phase 2 (YA and OA subset participants***)	Blood	-	79 mL	5 mL	69 mL	30 mL	10 mL*	70 mL*	263 mL
Phase 2 (non-subset YA participants)	Blood	-	30 mL†	-	-	30 mL†	30 mL*†	30 mL *†	120 mL
Phase 2 (non-subset OA participants)	Blood	-	10 mL	-	-	10 mL	10 mL*	10 mL*	40 mL

\* Blood samples should only be collected for participants who did not receive a standard of care vaccination against seasonal flu since their enrollment into the study.

\*\* Urine sample will only be taken for screening purposes in Phase 1.

\*\*\* Refer to Section 6.3 for subset description.

† Part of the blood samples might be used for assay development and validation.

### 8.2.2. Laboratory assays

**Table 11 Laboratory assays**

Test classification	System	Component	Challenge	Method	Laboratory*
Humoral immunity (Antibody determination)	Serum	CCI	CCI		GSK or GSK designated lab
	Serum				GSK or GSK designated lab
	Serum				GSK or GSK designated lab
	Serum				GSK or GSK designated lab
	Serum				GSK or GSK designated lab
	Serum				GSK or GSK designated lab

Test classification	System	Component	Challenge	Method	Laboratory*
	Serum CCI	CCI	CCI		GSK or GSK designated lab
	Serum				GSK or GSK designated lab
	Serum				GSK or GSK designated lab
			CCI		GSK or GSK designated lab
					GSK or GSK designated lab
	Whole blood CCI				GSK or GSK designated lab
Innate immunity	Plasma		N/A		GSK or GSK designated lab

Ab: antibody; CCI

; MN: microneutralization CCI

CCI ; N/A: not applicable; CCI .

\* Refer to the list of clinical laboratories for details.

\*\* CCI

† Only when possible.

**Clinical testing with assays** supporting tertiary endpoints where analyses might be deemed futile due to the other study results might not be performed.

Additional testing on collected samples (such as, but not limited to, CCI

might be done during or after the study if deemed necessary to gain a better understanding of the vaccine(s), ***of the clinical study data*** and/or of the disease. These additional assays may not be represented in the objectives/endpoints of the study protocol.

The addresses of clinical laboratories used for sample analysis are provided in a separate document accompanying this study protocol.

GSK clinical laboratories have established a Quality System supported by procedures. The activities of GSK clinical laboratories are audited regularly for quality assessment by an internal (sponsor-dependent) but laboratory-independent Quality Department.

### 8.2.3. Immunological read-outs

**Table 12** Immunological read-outs

Blood sampling timepoint		Subset name	Approximate No. of participants	Component	
Type of contact and timepoint	Sampling timepoint				
Day 1	Pre-dose	All enrolled participants (Phase 1 and Phase 2)	1272	CCI	
		Participants in exploratory immunogenicity subset (Phase 2)	400		
		For CCI [REDACTED] sample collection will be limited to selected sites.			
			400		
			400		
			400		
			400		
Day 2	Post-dose	Participants in exploratory immunogenicity subset (Phase 2)	400		
Day 8	Post-dose	Participants in exploratory immunogenicity subset (Phase 2)	400	CCI	
			400		
			400		
			400		
			400		
Day 29	Post-dose	All enrolled participants (Phase 1 and Phase 2)	1272		
		Participants in exploratory immunogenicity subset (Phase 2)	400		
		Participants in exploratory immunogenicity subset (Phase 2)	400		
Day 92	Post-dose	All enrolled participants (Phase 1 and Phase 2)	1272 ‡		

Blood sampling timepoint		Subset name	Approximate No. of participants	Component
Type of contact and timepoint	Sampling timepoint			
Day 183	Post-dose	All participants enrolled (Phase 1 and Phase 2)	1272‡	CCI
		Participants in exploratory immunogenicity subset (Phase 2)	400‡ 400‡ 400‡ 400‡	

Ab: antibody; CCI

\* Strains used to design the study intervention

\*\* CCI

‡ Given that samples will only be collected from participants who did not receive a standard of care vaccination against seasonal flu, this number represents the maximum number of participants who will have a sample collected for the Visit.

### 8.2.4. Immunological correlates of protection

CCI

### 8.3. Safety assessments

Planned timepoints for all safety assessments are provided in the SoA.

#### 8.3.1. Physical examination

1. During the screening visit (in Phase 1 only) and prior to dosing at Visit 1 (Day 1), the investigator will perform physical examination of the participant including assessment of resting vital signs: systolic/diastolic blood pressure, heart rate and respiratory rate after at least 10 minutes of rest, body weight and height. Vital signs are to be taken before blood collection for laboratory tests.
2. If the investigator determines that the participant's health on the day of study intervention administration temporarily precludes dosing, the visit will be rescheduled. Refer to the Section 5.5 for the list of criteria for temporary delay of study intervention administration.
3. If the participant reported any pre-existing medical condition, the investigator would extend the physical examination according to his/her medical judgment to ensure that the participant meets all the inclusion/exclusion criteria.

4. Treatment of any abnormality observed during physical examination must be performed according to local medical practice outside this study or by referral to an appropriate health care provider.
5. Physical examination at each study visit after the dosing visit, will be performed only if the participant indicates during questioning that there might be some underlying pathology(ies) or if deemed necessary by the investigator or delegate.

### **8.3.2. Pre-dosing body temperature**

The body temperature of each participant needs to be measured prior to the study vaccine administration and recorded in the eCRF. If the participant has fever on the day of dosing, the study intervention administration visit will be rescheduled. Refer to the SoA (Section 1.3) for the definition of fever for this study and preferred location for body temperature measurement.

### **8.3.3. Warnings and precautions to administration of study intervention**

Warnings and precautions to administration of study intervention must be checked at Visit 1 (Day 1) prior to dosing, as specified in SoA (Section 1.3).

Refer to the approved product label/package insert.

### **8.3.4. Myocarditis and pericarditis assessment and definitions**

All potential cases of myocarditis or pericarditis will undergo diagnostic work-up and be clinically evaluated.

To detect asymptomatic participants, cardiac troponin (Troponin I and/or Troponin T) testing will be performed for all study participants on Day 1, Day 8 and Day 29 in Phase 1 of the study. An abnormal cardiac troponin test on Day 8 or Day 29 will be repeated for confirmation.

Cardiac symptoms of myocarditis and/or pericarditis include the following: acute chest pain or pressure; palpitations; dyspnea after exercise, at rest or lying down; and diaphoresis. Non-specific symptoms may include fatigue, abdominal pain, dizziness or syncope, edema, cough, **cyanosis, weakness, shoulder and/or upper back pain, nausea, vomiting, diarrhea, altered mental status and low-grade intermittent fever** [SPEAC, 2022].

**Phase 1:** The following cases will be referred to a cardiologist or emergency room (as appropriate) for further evaluation and management following current practice guidelines (e.g., American Heart Association or local standard of care):

- Asymptomatic participants with elevated cardiac troponin values on Day 8 or Day 29 (confirmed on repeat testing) following a normal cardiac troponin value at baseline (Day 1), with no other identifiable cause of the finding.

- Symptomatic participants with  $\geq 1$  new or worsening cardiac symptom or  $\geq 2$  new or worsening non-specific symptoms within 4 weeks after dosing, with no potential alternative etiology, as assessed by the investigator [[SPEAC](#), 2022].

*Phase 2: Monitoring for asymptomatic participants by routine screening for elevated cardiac troponin will not be included in the Phase 2 part of the study. However, an expanded focus on symptom identification (including participant specific educational material), unscheduled study site visits for further evaluation, and an extended monitoring time period will be implemented as outlined below.*

- *Participants will be provided with educational materials, as part of the consent process, describing the signs and symptoms of myocarditis and pericarditis as well as guidance on how and when to seek medical care and contacting study personal.*
- *If the participant develops  $\geq 1$  new or worsening cardiac symptoms, and/or  $\geq 2$  new or worsening non-specific symptoms within 6 weeks after dosing with no potential alternative etiology, as assessed by the Investigator, an unscheduled study site visit will take place immediately (or an emergency room visit as per clinical judgment by the investigator) where a full physical examination, an ECG (if a study site does not have the capability to conduct an ECG, an alternative medical facility/qualified vendor can be used), screening of a cardiac biomarker (Troponin I and/or Troponin T), and screening of an inflammatory marker (CRP, erythrocyte sedimentation rate or D-dimer) will be done.*
- *If the ECG, the cardiac biomarker and/or the inflammatory marker results are abnormal with no potential alternative etiology, as assessed by the investigator, the participant will be referred to a cardiologist immediately (or an emergency room visit as per clinical judgment by the investigator) for further evaluation and management following current practice guidelines (e.g., American Heart Association or local standard of care).*

*Definitive, probable and possible cases of myocarditis/pericarditis (per Brighton case definitions [[SPEAC](#), 2022]) will be determined by the cardiologist and reported as an AESI. Participants will be followed-up until cardiac evaluation is completed, and/or symptoms have resolved, whichever comes later.*

*Definitive, probable and possible cases of myocarditis or pericarditis occurring in temporal association with vaccination of study participants will be submitted as expedited reports following suspected unexpected serious adverse reaction (SUSAR) reporting timelines.*

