**Table 2 Schedule of activities (SoA). Phase 2**

Type Of Contact	Visit 1	Visit 2*	Contact 1**	Contact 2	Visit 3†	Visit 4	Visit 5‡	Visit 6‡	Notes
Timepoints	Day 1	Day 2	Day 2	Day 3	Day 8	Day 29	Day 92	Day 183	
Informed consent	● a								See Section 10.1.3 for details
Inclusion and exclusion criteria	● a								Check clinical status before randomization and/or administration of study intervention. See Sections 5.1 and 5.2 for Inclusion and Exclusion criteria
Collect demographic data	●								See Section 8.1.1 for details
Medical and vaccination history	● a								See Section 8.1.2 for details
Physical examination	● a	○			○	○	○	○	Physical examination after Day 1 will be performed only if the participant indicates that there might be some underlying pathology(ies) or if deemed necessary by the investigator or delegate. See Section 8.3.1 for details
Urine pregnancy test (only for female participants of childbearing potential)	● a								Serum pregnancy test can be done as per local requirements if time allows. See Section 8.3.6 for details
Randomization	○ a								Country, study, center and flu vaccination history in the past 2 years will be used as minimization factor. Age group and sentinel status will be stratification factors. See Section 6.3 for details.
Check contraindications, warnings, and precautions to vaccination	○ a								See Section 8.3.3 for details
Check criteria for temporary delay for enrollment and/or study intervention administration	○ a								See Section 5.5 for details
Study group and intervention number allocation	● a								See Section 6.3 for details

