##### **8.4.1. Time period and frequency for collecting AE, SAE, and other safety information**

All SAEs will be collected from the day of study intervention administration (Day 1) until LSLV (Day 183) at the time points specified in the SoA. SAEs assessed as related to study participation (e.g., study intervention, protocol-mandated procedures, invasive tests, or change in existing therapy) or related to a GSK product (non-IMP) will be recorded from the time a participant consents to participate in the study.

All AEs will be collected from the start of study intervention until Day 7 (for solicited events) or Day 28 (for unsolicited events) at the timepoints specified in the SoA.

Medical occurrences that begin before the start of study intervention but after obtaining informed consent will be recorded as medical history/current medical conditions, not as AEs.

Complete list of safety events to be collected in this study and the timeframes for their collection and reporting are provided in [Table 15](#).

***Investigators are not obligated to actively seek information on AEs or SAEs after conclusion of the study participation. However, if the investigator learns of any SAE, including a death, after a participant has been discharged from the study, the investigator must record it in the medical records. If the investigator considers the event to be reasonably related to the study intervention or study participation, the investigator must promptly notify the sponsor.***

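### In Phase 2 the myocarditis/pericarditis symptom trigger runs to 6 weeks, but prompted symptom collection was not extended with it, so the last 6 to 13 days rest on unprompted participant reporting

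*Protocol*

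**What the plan says.** Protocol Section 8.3.4 states for Phase 2: "Monitoring for asymptomatic participants by routine screening for elevated cardiac troponin will not be included in the Phase 2 part of the study". In its place it relies on symptom identification and unscheduled visits, and adds that "an extended monitoring time period will be implemented as outlined below". The means then described is participant education: "Participants will be provided with educational materials, as part of the consent process". The Phase 2 schedule of activities (Table 2) places consent at Visit 1, Day 1.

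The trigger is at least one new or worsening cardiac symptom and/or at least two "new or worsening non-specific symptoms within 6 weeks after dosing with no potential alternative etiology", as assessed by the investigator. When it is met, "an unscheduled study site visit will take place immediately" (or an emergency room visit if the investigator judges so), with physical examination, ECG, troponin and an inflammatory marker. The corresponding Phase 1 criterion covers "new or worsening non-specific symptoms within 4 weeks after dosing".

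General AE collection keeps its own limits. Section 8.4.1 says: "All AEs will be collected from the start of study intervention until Day 7 (for solicited events) or Day 28 (for unsolicited events"). Section 10.3.5.2 confines eDiary entry of unsolicited events, and the automatic reminder, to Day 1 to Day 28. The site notification in Section 10.3.4 is generated by the eDiary. Under Section 10.3.5.1 the device is returned at Visit 4 or the application is removed after Day 29. Table 2 marks non-serious AE recording up to Visit 4 only. MAEs, SAEs and AESIs are marked at every visit or contact through Day 183.

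**The concern.** The longer symptom window is part of what Phase 2 offers for this AESI, and the protocol wants the work-up to be immediate. The tools that prompt a participant to mention a symptom end at Day 28 or at Visit 4, and no contact is scheduled in the remainder of the window.

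Recording AESIs to Day 183 does not fully cover this. Section 8.4.4.2 keeps symptoms that might lead to the diagnosis as ordinary AEs until the diagnosis is made. A trigger symptom that starts after Visit 4, is not serious and does not lead the participant to seek care therefore falls outside every category still marked at Visits 5 and 6.

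What is at stake is timing. An ECG and troponin taken weeks after onset are not the assessment that Section 8.3.4 intends. Holding rule 1d (Table 14) and the expedited reporting in Section 8.3.4 both depend on a case being identified, though the holding rule matters only while dosing continues.

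**Working it through.** This is a day count. The plan states no figure of its own to reproduce, and no sample size, power or alpha is involved.

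**Inputs**
- Trigger window: 6 weeks after dosing (Section 8.3.4, Phase 2).
- Day convention: the 28-day follow-up is Day 1 to Day 28 inclusive (Table 5), so 6 weeks is Day 1 to Day 42.
- Visit intervals are differences between dates (Table 4), so study day = interval + 1. Visit 4 at 28–35 days is Day 29–36. Visit 5 at 84–98 days is Day 85–99.
- eDiary entry and reminders: Day 1 to 28 (Section 10.3.5.2).
- Group sizes: 8 groups of 120, of which 6 are mRNA and 2 control (Section 4.1).

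**Days without prompting**
1. No eDiary prompt: Day 29–42, 42 − 28 = 14 days. Visit 4 falls within this stretch and offers one occasion for questions.
2. After Visit 4 there is neither prompt nor contact. Visit 4 on Day 29: 42 − 29 = 13 days (13/42 = 31%). Visit 4 on Day 36: 42 − 36 = 6 days (6/42 = 14%).
3. If 6 weeks is read as 42 elapsed days, the counts are 42 − 28 = 14 and 42 − 35 = 7.

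**Time from onset to the next scheduled contact**
- Shortest: onset Day 42, Visit 5 on Day 85, 85 − 42 = 43 days.
- Longest: onset Day 30, Visit 5 on Day 99, 99 − 30 = 69 days.
- With Visit 4 on Day 29 and Visit 5 on the planned Day 92: 92 − 42 = 50 to 92 − 30 = 62 days.

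These delays assume that the symptom comes up at Visit 5. Table 2 does not mark ordinary non-serious AEs there.

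**Effect of one remote contact, for participants who reply**
- Contact on Day 43: 43 − 42 = 1 to 43 − 30 = 13 days from onset.
- Contact on Day 44: 44 − 42 = 2 to 44 − 30 = 14 days.

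**Population:** 8 × 120 = 960 participants (6 × 120 = 720 mRNA, 2 × 120 = 240 control).

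**What cannot be computed:** the number of delayed work-ups, and the number of extra work-ups that a fix would generate. The documents give no myocarditis rate, onset-time data or background frequency of the listed symptoms.

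**The case against.** The strongest reply is that Phase 2 plans more for weeks 5 and 6 than Phase 1 did. Phase 1 troponin was tested on Days 1, 8 and 29 only, and its symptom window closed at 4 weeks. Phase 2 adds a trigger, education and a defined work-up for those weeks. Participant-initiated reporting is the mechanism Section 8.3.4 states, and eDiary entries in Day 1 to 28 are also self-report (Section 8.1.3). The educational material is not among the documents, so it may already state the 6-week limit. The note to Section 2.3.1 does not class myocarditis/pericarditis as an important potential risk for this candidate, and Section 4.3.2 (partly redacted) reports no Phase 1 safety signal.

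Most of this stands, and it rules out several stronger inferences:
- A reader might infer that dropping troponin screening opened the gap. It did not: the Phase 1 tests gave no planned cover after Day 29.
- A reader might set Phase 1's zero uncovered days against 6 to 13 in Phase 2 and conclude that Phase 2 is weaker. The zero only reflects the shorter window.
- A reader might infer that cases will be lost. MAEs, SAEs and AESIs are recorded to Day 183, an unscheduled visit under Section 8.3.4 itself fits the MAE definition, and AEs already recorded continue to be followed (Section 10.3.5.6).
- A reader might see two sections in conflict. A symptom trigger and a general AE collection period serve different purposes and can have different lengths.

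The reply does not show that anything prompts a participant between Visit 4 and Day 42. The difference between prompted and unprompted reporting remains. It matters most for symptoms on the list such as fatigue, cough or weakness, which people may not think to report.

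**Conclusion.** The point holds as a minor, inexpensive improvement in safety ascertainment, not as a contradiction or an error. For 6 to 13 of the 42 window days, detection of a trigger symptom depends on the participant raising it unprompted, with support only from the Day 1 material and the participant card. The gap covers symptoms that start after Visit 4, have no alternative cause, and are neither volunteered nor medically attended. For those, the next scheduled contact is 43 to 69 days after onset.

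The counts rest on the protocol's inclusive day convention; the elapsed-day reading moves them by one day and changes nothing of substance. The conclusion also assumes that the educational material is not reissued after Day 1, since no repeat is planned in the documents. Nothing in them shows that onset in weeks 5 and 6 is frequent. The case for acting is that the sponsor chose to monitor those weeks and the remedy is cheap.

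**What to change.** (a) At Visit 4, give participants the existing Section 8.3.4 material again and remind them that trigger symptoms are to be reported immediately through 6 weeks after dosing.

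(b) In Section 8.4.1, Table 15 and the Phase 2 schedule of activities, record Section 8.3.4 trigger symptoms with onset to Day 42. Keep these records separate from the Day 1 to 28 co-primary unsolicited-AE endpoint, so that its tabulations in SAP Section 4.2.1.2 are unchanged.

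Optional: one remote contact at about Day 43, by a route already allowed in Table 2 (telephone, SMS or email), with an open question in keeping with Section 8.4.2. It comes after the window closes, so it would not make the visit immediate, and it shortens the delay only for those who reply. It should not be presented as guaranteeing a two-week maximum. Sending it to about 960 people is a matter of judgment.

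The trigger, the work-up, the sample size and the planned analyses stay as they are. The cost is a protocol amendment, which may need ethics and health-authority approval (Section 10.1.1), a little site time, and some additional work-ups. Their number is unknown, because two non-specific symptoms without another cause are enough to require a visit.
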